5.3.6.1. Digit Symbol Substitution Test (DSST) - MCI Subjects

The DSST integrates complex neuropsychological processes and measures aspects of cognitive function, including cognitive and psychomotor speed, attention, visual scanning, and executive function.

The specific version of the DSST used in this study is the Coding subtest of the Wechsler Adult Intelligence Scale - 4th edition (WAIS-IV).

Subjects are asked to copy simple graphic symbols that are paired to the digits 1–9 within a specified time period. Using a key, the examinee is asked to draw each symbol under its corresponding number. The examinee's score is determined by the number of symbols correctly drawn within a 120-second time limit. The maximum attainable score is 135, with higher scores indicating better performance. Test scores can be benchmarked against published normative data

by age group, and education level (2008 NCS Pearson, Inc., [Gaertner 2018](#)) as a means of evaluating test performance.

5.3.6.2. **Dementia Cognitive Fluctuation Scale (DCFS) – DLB and PDD Subjects**

The DCFS is a 17-item informant completed questionnaire that queries confusion (3 questions), differences in functioning through the day (1 question), sleep patterns and problems (6 questions), varying levels of alertness (4 questions) and clarity of thought/communication (3 questions). Five of the items proved discriminatory between Lewy body dementias, PD and AD (items 4, 10,11,12, and 14; range of function differences during the day; REM sleep disorder; daytime sleeping; daytime lethargy/drowsiness despite adequate sleep; level of consciousness throughout the day). The reduced scale comprised of the 5 items that are sensitive and specific to the reliable identification of cognitive fluctuations in Lewy body dementias ([Lee 2014](#)).

5.3.6.3. **Modified Hoehn and Yahr Scale (MHYS) – RBD+PD, DLB and PDD Subjects**

The MHYS is a clinician-completed rating scale that is used to describe the symptom progression of PD. Originally described in 1967, it parsed the progression of PD into 5 stages. It has since been modified with the addition of stages 1.5 and 2.5 to account for the intermediate course of PD ([Fahn 1987](#)). As such, the MHYS is as follows:

- Stage 0: No signs of disease;
- Stage 1.0: Unilateral disease;
- Stage 1.5: Unilateral plus axial involvement;
- Stage 2: Bilateral disease, without impairment of balance;
- Stage 2.5: Mild bilateral disease, with recovery on pull test;
- Stage 3: Mild to moderate bilateral disease; some postural instability; physically independent;
- Stage 4: Severe disability; still able to walk or stand unassisted;
- Stage 5: Wheelchair bound or bedridden unless aided.

5.3.6.4. **Hospital Anxiety and Depression Scale (HADS) – MCI and RBD+PD Subjects**

HADS is a 14-item questionnaire with subscales for anxiety and depression. It was originally developed to screen for depression and anxiety in a hospital setting but was later validated for use in a general population. The subjects are given 14 questions in multiple-choice format, seven about depressive symptoms (HADS-D) and seven about anxiety symptoms (HADS-A) and are asked to give a score from 0 to 3 where 0 is the least depressed/anxiety option and 3 the most. A total score ≥ 12 suggests depression, whereas sub-scores of ≥ 8 suggest anxiety or depression ([Bjelland 2002](#); [Kjaergaard 2014](#)).

5.3.6.5. **REM Sleep Behavior Disorder Single-Question Screen (RBD1Q) - RBD+PD Subjects Only**

The RBD1Q is a single “yes-no” question that queries the classic dream-enactment behavior of RBD ([Postuma 2012](#)).

The RBD1Q consists of a single question, answered “yes” or “no,” as follows: “Have you ever been told, or suspected yourself, that you seem to ‘act out your dreams’ while asleep (for example, punching, flailing your arms in the air, making running movements, etc.)?”

5.3.6.6. **Montreal Cognitive Assessment (MoCA)**

The MoCA ([Nasreddine 2005](#)) is a brief cognitive screening tool that is used in clinical research and practice. The scores range from 0 to 30 with scores lower than 26 suggesting cognitive disorder. The MoCA includes measures of expressive and receptive language, memory, and praxis. There are items that screen executive functions and working memory.

5.3.6.7. **Epworth Sleepiness Scale (ESS)**

The ESS is an 8-item, self-administered questionnaire in which subjects are asked to rate, on a 4-point scale (0-3), their usual chances of dozing off or falling asleep while engaged in 8 different activities. The total score is the sum of the 8 item scores, with scores ranging from 0 (no daytime sleepiness) to 24 (high sleep propensity in daily life).

5.3.6.8. **Geriatric Depression Scale (GDS)**

The GDS is a 30-item self-administered yes/no question test constructed for brief screening of depression in elderly persons ([Yesavage 1982-1983](#)). Scores greater than 9 are considered suspect for depression.

5.3.6.9. **Sustained Attention to Response Task (SART) -- DLB and PDD Subjects at Select Sites Only**

The Sustained Attention to Response Task (SART) is a computer-based go/no-go task that requires participants to withhold behavioral response to a single, infrequent target (often the digit 3) presented amongst a background of frequent non-targets. There is evidence supporting the role of the SART as a measure of working memory, sustained attention, and impulse/inhibitory control. In this task, the participant is asked to respond (e.g., button press) to the non-target and to inhibit their response to the target. To perform well, individuals must remain sufficiently attentive to their responses, such that, at the appearance of a target, they can override the dominant pre-potent motor response and substitute the directly antagonistic response (i.e., withhold button press) ([Phillips 2020](#)).

5.3.6.10. **Freezing of Gait Questionnaire — RBD+PD, DLB and PDD Subjects Only**

Freezing of Gait (FOG) is one of the most frequent and disabling symptoms in Parkinson’s disease (PD) affecting about half of all patients, especially in the advanced stages of disease. The Freezing of Gait Questionnaire (FOG-Q) is considered a valid and reliable tool for the assessment of FOG severity. The FOG-Q consists of six items borrowed from the Gait and Falls Questionnaire ([Giladi 2000](#)).

5.3.6.11. **Verbal Fluency Test**

Verbal fluency tests are widely used for assessing executive function and require the generation of words from initial letters (phonological verbal fluency) or belonging to a specific category (semantic fluency), under a time constraint.

The specific versions of verbal fluency used in this study are the ‘ALPHABET’ and ‘CATEGORY’ tests from the Brief And Simple Index of Cognition (BASIC) (Harrison 2000).

For the ALPHABET task, subjects are given 1 minute to say aloud as many words they can think of that begin with the letter F, avoiding repetitions or the same words with different endings. The total score is the number of correct words generated.

For the CATEGORY task, subjects are given 1 minute to say aloud as many animals they can think of, avoiding repetitions. The total score is the number of animals generated.

5.3.7. CANTAB Assessments

The CANTAB is a standardized and automated administration of cognitive testing via touch tablet, which will include the following:

- The Reaction Time (RTI) task is a processing and psychomotor speed task. It begins with a simple stage with only one target and can be increased to 5 targets to increase demand. Once a yellow circle flashes on screen, subjects must select that circle as fast as possible.
- The Verbal Recognition Memory (VRM) Phase I and Delayed Verbal Recall recognition measures the ability to encode and subsequently retrieve verbal information. Eighteen (18) words are presented, and subjects are subsequently asked to recall them; this is repeated 2 times. Forty-five (45) minutes later free recall test and forced-choice recognition test are carried out.
- The Adaptive Tracking Task (ATT) measures visuomotor coordination and vigilance. In this test, a small circle (target) will continuously move across the screen in a semi-randomized fashion, so as to minimize the subject’s ability to predict the trajectory of the target. The subject is instructed to use his/her finger upon the touch screen to move a small dot so that it is consistently within the center of the moving target on the screen. During the test, the speed of the circle is adjusted in response to the subject’s ability to keep the dot in the circle, ensuring that the test is adapted to the individual subject.
- The Paired Associates Learning (PAL) task is a measure of visuo-spatial episodic memory relying on the functional integrity of the hippocampus. The task becomes gradually more difficult, benchmarking a subject’s memory capacity. Subjects have to remember the location of an abstract pattern in a specific location.
- The Rapid Visual Information Processing (RVP) task is a sensitive measure of sustained attention, outputting measures of response accuracy, target sensitivity and reaction times. For the RVP task single digits appear in a pseudo-random order at a rate of 100 digits per minute in box in the center of the screen. Subjects must detect a series of 3-digit target sequences (3-5-7; 2-4-6; 4-6-8) and respond by touching the button at the bottom of the screen when they see the final number of the sequence. Nine target sequences appear every minute.
- The Stop Signal Task (SST) measures response inhibition (impulse control). The subject must respond to an arrow stimulus, by selecting one of two options, depending on the direction in which the arrow points. If an audio tone is present, the subject must withhold making that response (inhibition).

5.3.8. Pupillary Light Reflex (PLR) Test

The pupillometry measurements (PLR) will be completed in a room where ambient noise and lighting will be controlled and uniform. After resting for 5 min, and before and after receiving the study drug on Day 1 of Treatment Periods 1 and 2, the pupillometry measurements (repeated once) will be taken from each eye using a pupilometer with an opaque rubber cup covering one eye. Each pupillometry session measuring both eyes is about 1 minute. There is no need for a break between measurements.

On Day 7 and Day 14 of Treatment Periods 1 and 2, additional PLR tests will be performed, as per [Schedule of Events](#).

Effects of treatment on pupillary light reflex include one or more of the following measures: pupil area, baseline pupil diameter (BPD), maximum constriction velocity (MCV), absolute constriction amplitude (ACA), maximum dilation velocity (MDV), time to reach 75 % of initial resting diameter during pupillary dilation ($T^{3/4}$), and dilation velocity at $T^{3/4}$ ($DV^{3/4}$).

5.3.9. Neuromelanin MRI Scan

Neuromelanin MRI will be measured to evaluate its suitability as a biomarker of noradrenergic regions in the brain such as the LC. The neuromelanin MRI scan will be performed once, and may be done at any time during the study. The procedure is optional since it is dependent upon on imaging center access and the capabilities of the MRI facility.

Neuromelanin is a dark insoluble complex that is synthesized as an oxidative byproduct of dopamine and noradrenaline in regions of high catecholamine activity such as the substantia nigra and LC ([Wakamatsu 2015](#)). It sequesters potentially toxic organic chemical, exogenous and endogenous metals such as iron. When bound to metals such as iron and copper, neuromelanin is highly paramagnetic, leading to T1-shortening and hyperintense signal on T1-weighted turbo spin-echo MRI sequences. As a result, neuromelanin can be detected by non-invasive MRI methodology.

The neuromelanin MRI will require the subject to lie in the MRI scanner for about 30 minutes.

5.3.10. Electroencephalogram (EEG) – DLB and PDD Subjects

EEG data will be collected in subjects at resting state with eyes open and eyes closed and during the administration of the SART (at selected site(s)) using a Stat X24 EEG system. Stat X24 offers 20 channels of high-quality EEG. Channels include sites: Fz, Fp1, Fp2, F3, F4, F7, F8, Cz, C3, C4, Pz, P3, P4, POz, T3, T4, T5, T6, O1, O2. Referencing is acquired through linked mastoids. Each EEG acquisition will be approximately 5 minutes in length for a total of 10 minutes. For eyes open data collection, the subject will be instructed to focus on a cross on the screen while seated and relaxed. For eyes closed, the subject will be instructed to sit, relaxed with eyes closed but do not fall asleep. The absolute and relative power spectral densities (PSDs) will be calculated for each 1 second epoch (1-59 Hz bins), and also grouped into the standard EEG bandwidths: delta, theta, alpha, beta, and gamma. Additionally, the PSD variables will be averaged across brain regions of interest, including frontal, central, parietal, temporal, and

occipital. Previous data suggests EEG slowing was correlated with CFs, measured by the clinician assessment of fluctuations (CAF) scale ([Stylianou 2018](#)).

5.3.11. Facial Expression Recognition Task (FERT) – MCI and RBD+PD Subjects

The Facial Expression Recognition Task assesses the recognition of facial emotions. Faces with six different basic emotions (happiness, fear, anger, disgust, sadness, surprise) are briefly displayed on the screen and participants are required to indicate the expression of the face via a button-press. Different intensity levels of each emotion are presented, which increases the ambiguity of the facial expression and the sensitivity of the task. Early change in measures of emotional bias in depressed patients treated with antidepressants has been positively correlated with the improvement in patients' symptoms of depression across a full 6–8 weeks of treatment ([Tranter 2009](#)) suggesting that such early changes detected through the use of the FERT may be predictive of antidepressant response.

5.3.12. BioStamp nPoint Data Collection

The BioStamp nPoint device is a wireless remote monitoring system intended for use by researchers and healthcare professional for continuous collection of physiological, activity and sleep data in home and professional healthcare and home settings. These data include heart rate, heart rate variability, respiration rate, activity (including step count and activity classification), and posture (body position relative to gravity). Data are transmitted wirelessly from the Sensors for storage and analysis. Four key measures of interest will be evaluated:

- Activity and posture classifications, durations, and temporal patterns
- Sleep (duration, posture transitions, and activity counts)
- Autonomic function – heart rate variability (HRV)
- Temporal pedometry (daily step count, and gait cadence)

Once all screening visit procedures are completed and the subject meets all eligibility criteria, the BioStamp nPoint device will be dispensed to the subject, who will be instructed to wear it for 7 days during the Lead-In Period. The BioStamp device will be re-dispensed at 2 other timepoints (at each of the Day 1 Visits in Treatment Periods 1 and 2), worn for 14 days and removed on Day 14 in each period.

The BioStamp nPoint device will include the BioStamp sensors, Link Hub, Link App mobile phone, adhesive stickers, and applicator guide. At the time of dispensing the BioStamp nPoint device, written instructions and training videos will be provided to the subject.

5.4. Concomitant Medications

Subjects who required routine medication to manage and treat concurrent conditions (e.g., hyperlipidemia, diabetes, hypertension) must be on stable doses 3 months prior to Screening. Any concomitant therapy taken from the time the subject signs the informed consent through the final visit must be recorded on the CRF for all enrolled subjects. The medication name, dosage, date, and indication for use must be recorded. The Medical Monitor or designee should be

notified in advance of (or as soon as possible after) any instances in which prohibited therapies are administered.

Prohibited concomitant medications include the following:

- Paracetamol >2 g per day
- PD medication changes within 3 months prior to Screening (applicable to RBD+PD, DLB and PDD subjects)
- Vitamin E >400 IU daily
- Aspirin >300 mg daily
- Cannabis and products containing THC and/or CBD
- Melatonin or hypnotics, such as Zolpidem or Zopiclone, within 48 hours prior to a study visit involving cognitive testing
- Levodopa >1.5 g daily
- Changes in clonazepam and monoamine oxidase inhibitor (MAOI) dosing within 4 weeks before Screening.
- Use of St. John's Wort or Ginkgo Biloba within 48 hours prior to study enrollment (defined as the Lead-in Period).
- Use of benzodiazepine (except clonazepam) is prohibited from Screening throughout the study.
- Use of gabapentinoids, phenylephrine and pseudoephedrine are prohibited from Screening throughout the study.
- Prior treatment with any β -AR agonists or β -AR blockers (includes oral medications, eye drops with adrenergic agents such as timolol or atenolol, IV, or inhaled), or any meds that impact adrenergic signaling within the last month prior to Screening will exclude a subject from study enrollment. Use of β -AR agonists or β -AR blockers is not allowed during the study.
- Subjects who had prior treatment with any investigational drug ≤ 90 days prior to dosing (Day 1), or ≤ 5 half-lives of the drug (whichever is longer) will be excluded.
- Subjects should not receive the influenza vaccine within 2 weeks of the Screening visit through to the Follow-Up Visit.
- Opioid use is prohibited within 1 month prior to Screening and during the study.

5.5. Escape/Rescue Medications

Since CST-103 is being co-administered with the nonselective β -AR antagonist nadolol (CST-107), the typical β -AR agonist effects such as HR increases, and hypokalemia are unlikely to occur. However, if there are intolerable HR/BP increases subjects may be administered the lowest commercially available dose of nadolol or equivalent β -AR antagonist. Nadolol has been successfully used at low doses (5 mg or less) in previous CuraSen studies to block the peripheral effects of CST-103 and other β -AR agonists. The blood pressure and heart rate increase at which treatment is given will be based on clinical judgment of the study physician and the PI. If

hypokalemia is detected, subjects should be managed based on clinical needs and presentation as appropriate per the Investigator's discretion.

5.6. Contraception

Female subjects of childbearing potential (i.e, not postmenopausal or not surgically sterile) and all male participants with sexual partners of childbearing potential must use reliable methods of birth control during their participation in the study.

Unless confirmed to be azoospermic (vasectomized or secondary to medical cause), male subjects must agree to use a male condom from Day 1 throughout the study when having penile-vaginal intercourse with a woman of childbearing potential who is not currently pregnant. Men with a pregnant or breastfeeding partner must agree to remain abstinent from penile-vaginal intercourse or use a condom during each episode of penile-vaginal penetration until after the Follow-Up Visit.

Female subjects of childbearing potential who have a male partner must agree to contraception from Screening through 30 days after the last administration of study medication.

Acceptable methods of contraception for female subjects of child-bearing potential study include the following:

- Use a reliable method of birth control, including hormonal prescription oral contraceptives, contraceptive injections, contraceptive patch, contraceptive implant, contraceptive ring, intrauterine device, intrauterine hormone-releasing system, barrier method (e.g., condoms, or diaphragm, or cervical cap when used with spermicide), or
- monogamous relationship with a male partner of confirmed sterility, or
- Practice complete abstinence, i.e., refrain from sexual intercourse.

Periodic abstinence (calendar, symptothermal, post-ovulation methods), withdrawal (coitus interruptus), spermicides only, and lactational amenorrhoea method are not acceptable methods of contraception.

The reliability of sexual abstinence needs to be evaluated in relation to the duration of the clinical trial and the preferred and usual lifestyle of the subject.

Females of non-childbearing potential may be enrolled if it is documented that they are postmenopausal (amenorrhea for ≥ 12 months) and follicle-stimulating hormone (FSH) ≥ 25 IU/L, or have undergone surgical sterilization, including hysterectomy, bilateral oophorectomy, bilateral salpingectomy, or Essure procedure. Females with FSH < 25 IU/L must agree to contraception from Day 1 through 30 days after the last administration of study medication, if they have a male partner.

6. ASSESSMENT OF SAFETY

6.1. Adverse Events

6.1.1. Definitions

Adverse Event

An AE is any untoward medical occurrence associated with the use of a study drug in humans and which does not necessarily have a causal relationship with this treatment. AEs may be reported by the subject, discovered through Investigator questioning, or detected through physical examination, laboratory test, or other means.

AEs include:

- Any new undesirable medical experience or an unfavorable and unintended change of an existing condition that occurs during or after treatment, whether or not considered related to study medication.
- Abnormal laboratory findings considered by the Investigator to be clinically significant, i.e., those that are unusual for the population being studied or individual subject.
- Complications and termination of pregnancy; uncomplicated pregnancies are not considered AEs but must still be reported.

Additionally, events (including intercurrent illnesses) occurring from the time of first dose will be documented on the AE CRF. Concurrent illnesses, which existed prior to first dose into the clinical trial, will not be considered AEs unless they worsen during the treatment period.

Serious Adverse Event

An SAE is defined as any untoward medical occurrence that at any dose:

- Results in death
- Is life-threatening (this means that the subject is at risk of death at the time of the event; it does not mean that the event hypothetically might have caused death if it were more severe)
- Requires or prolongs subject hospitalization
- Results in persistent or significant disability or incapacity
- Is a congenital anomaly or birth defect
- Is an important medical event that does not otherwise meet the criteria for seriousness

Medical and scientific judgment should be exercised in deciding if an event is serious if it does not meet the above definitions, such as an important medical event(s) that may not be immediately life-threatening or result in death or hospitalization but that may jeopardize the subject or may require intervention to prevent one of the above outcomes. Specific examples of such events are intensive treatment in an emergency room or at home for allergic bronchospasm, blood dyscrasias, or convulsions that do not result in hospitalization.

A distinction should be drawn between seriousness and severity of an AE. An AE that is assessed as severe, for example, should not be confused with an SAE. Severity is a category

utilized for rating the intensity of the event (see below); both AEs and SAEs will be assessed for severity grading. An event is defined as “serious” when it meets one of the predefined outcomes as described above.

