	
pacemakers, defibrillators, or other active implantable devices.
 
20. Known allergies or hypersensitivities to adhesives or hydrogel.
 
21. Females who are breastfeeding.
 
22. Any other reason for which the PI considers it is not in the best interest of the participant to undertake the study.
 
23. Inability to undergo a clinical MRI of the brain due to claustrophobia, inability to lie supine for a prolonged time period, or other contraindications to undergoing an MRI of the brain including, but not limited to, pacemakers; implantable cardioverter defibrillators; cochlear implants; cerebral aneurysm clips; implanted infusion pumps; implanted nerve stimulators; metallic splinters in the eye; and, other magnetic, electronic or mechanical implants or clinical findings that in the judgment of the investigator would pose a potential hazard in combination with MRI. (NOTE: this is a procedural exclusion not a study exclusion).

Description of Study Medications
	
The study medications will be provided as oral capsules for CST-103, CST-107 and corresponding matching placebos.
 
During Treatment Periods 1 and 2, subjects will receive once daily oral doses of 80 µg CST-103 or matching placebo co-administered with 1 mg CST-107 or matching placebo on Days 1 – 14.
 
A 14-day supply of study drug will be dispensed to the subject at the beginning of each treatment period, and the subject will be instructed to self-administer daily.

Study Duration
	
The study duration will be approximately 12 weeks, which includes a Screening period of up to 21 days, a Lead-In Period of up to 14 days, the treatment/study period of 6 weeks (two 2-week treatment periods separated with a 2-week wash-out), and the Follow-Up Visit 2 weeks after the last study drug dose.

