3. STUDY DESIGN

3.1. Clinical Trial Design

This is a Phase II, randomized, placebo-controlled, double-blind, crossover study on the CNS and pharmacodynamics effects of CST-103 co-administered with CST-107 in 4 subject populations with Neurodegenerative Disorders.

Approximately 40 subjects (approximately 20 subjects in Cohort A with RBD+PD or MCI and approximately 20 subjects in Cohort B with PDD or DLB) will be enrolled in a 2 period, 2-way cross over design following study eligibility confirmation during the screening period. The number of subjects enrolled in each cohort may change as emerging data are reviewed from this and other studies.

During each treatment period, subjects will receive daily doses of CST-103 co-administered with CST-107 or matching placebo for 14 days. Each treatment period will be separated by a washout period of 14 days (+5-day window).

All subjects will complete clinical and pharmacodynamic assessments during each treatment period and at the Follow-Up Visit as indicated in the [Schedule of Events](#).

PK blood samples will be collected prior to, during and after study medication administration, as indicated in the [Schedule of Events](#).

Pharmacodynamic blood samples will be collected as indicated in the [Schedule of Events](#) to investigate the effects of CST-103 co-administered with CST-107 on inflammatory biomarkers.

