6.1.2. Assessment of Adverse Events

Each event recorded on the AE CRF will be assessed by the Investigator with regard to the following categories.

Severity

Severity of AEs will be graded as one of:

- **Mild:** Awareness of signs or symptoms but easily tolerated. A type of AE that is usually transient and may require only minimal treatment or therapeutic intervention. The event does not generally interfere with usual activities of daily living.
- **Moderate:** A type of AE that is usually alleviated with additional specific therapeutic intervention. The event interferes with usual activities of daily living, causing discomfort but poses no significant or permanent risk of harm to the research subject.
- **Severe:** Incapacitating the ability to do work or to do activities. A type of AE that interrupts usual activities of daily living, or significantly affects clinical status, or may require intensive therapeutic intervention

Relationship to Study Medication

The Investigator or designee, using clinical judgment, will assess the causality/relationship between each AE and the most recently administered study medication (i.e., whether there is a reasonable possibility that the drug caused the event) and record that assessment in the CRF.

Unrelated: The AE is clearly not related to the study medication. The AE is clearly explained by another cause, or exposure to the study medication has not occurred.

Related: The AE may be related to the study medication. The AE and administration of the study medication are considered reasonably related in time, but the AE is more likely explained by the study medication than another cause.

AE reporting will extend from randomization until completion of the Follow-Up Visit. AEs occurring after the end of the clinical trial must be reported if the Investigator considers there is a causal relationship with the study medication.

All AEs, regardless of the relationship to study medication, will be recorded in the CRF.

All reports should contain a brief description of the event, date of onset, date of resolution, severity, treatment required, relationship to study medication, outcome, and whether the event is classified as serious. Whenever possible, the Investigator should group signs or symptoms that constitute a single diagnosis into a single event term. For example, “cough, rhinitis, and sneezing” might be grouped together as “upper respiratory tract infection.”

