### 10.1. Adverse Events

Adverse events (AEs) will be recorded from the signing informed consent through end of study. AEs will also be assessed for severity, relationship to study drug, and seriousness. AEs will be considered treatment-emergent if their onset occurs following the date of first dose up to the study completion date. Each TEAE will also be categorized according to the treatment period in which it occurs, in order to attribute and summarize an AE based on treatment received at time of event (i.e., during placebo or active treatment). Events that occur during the washout period between Treatment Period 1 and 2 will be attributed to the treatment received in Period 1, and events occurring after Treatment Period 2 up to the End of Study visit will be attributed to the treatment received in Period 2.

Any missing severity assessments will be assumed to be severe, missing relationship assessments will be assumed to be related, and missing seriousness assessments will be assumed as serious.

An overview of AEs will be produced, including counts and percentages of subjects with any incidences of: treatment-emergent AEs (TEAEs), serious AEs (SAEs), related AEs, unrelated AEs, AEs by maximum severity, AEs leading to treatment withdrawal and AEs leading to death.

Sponsor: CuraSen Therapeutics, Inc.  
Protocol Number: CST103/CST107-CLIN-011  
Version and Date: [REDACTED] v1.0 / 24May2022

Adverse events will be coded based on the Medical Dictionary for Regulatory Affairs (MedDRA 23.1) for reporting by system organ class (SOC) and preferred term (PT) in descending order of overall incidence.

Summaries of adverse events by SOC and PT will include the following types:

- TEAEs;
- SAEs; and
- Related AEs.

A summary of TEAEs by SOC, PT, and maximum severity will also be prepared.

A comprehensive listing of all AEs will be provided in a by-subject data listing. In addition, the following listings will be provided:

- SAEs;
- Related AEs; and
- AEs leading to study drug termination

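### Protocol 6.1.1 gives opposite answers on whether non-serious worsening of a pre-existing illness after dosing is an adverse event

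*Protocol*

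**What the plan says.** Three statements in Protocol 6.1.1 bear on this.

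- The first bullet of the AE definition includes "an unfavorable and unintended change of an existing condition that occurs during or after treatment", whether or not it is related to study medication.
- The sentence on documentation says "events (including intercurrent illnesses) occurring from the time of first dose will be documented on the AE CRF".
- The sentence that closes the AE definition says "Concurrent illnesses, which existed prior to first dose into the clinical trial, will not be considered AEs unless they worsen during the treatment period".

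Protocol 6.1.2 sets the reporting window: "AE reporting will extend from randomization until completion of the Follow-Up Visit". Protocol 8.8.5 treats every AE on or after first dose as treatment emergent and assigns those starting before the first Period 2 dose to the Period 1 treatment. SAP 10.1 agrees: "Events that occur during the washout period between Treatment Period 1 and 2 will be attributed to the treatment received in Period 1". It assigns events after Period 2 to the Period 2 treatment.

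The term at issue is used in two ways. Protocol 3.1 says "During each treatment period, subjects will receive daily doses of CST-103 co-administered with CST-107 or matching placebo for 14 days" and names the washout separately. The Study Duration entry of the synopsis refers to "the treatment/study period of 6 weeks (two 2-week treatment periods separated with a 2-week wash-out", which takes the washout in.

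**The concern.** Every subject enters with a neurodegenerative disease, and the primary objective names depressive symptoms in Cohort A and cognitive fluctuations in Cohort B. Worsening of something already present is therefore a foreseeable kind of event in this trial. (Section 6.1.1 itself names no condition; these are examples.)

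The closing sentence is the one specific to pre-existing illness, so a site could reasonably let it govern. If it does, a non-serious decline that begins after dosing stops does not qualify as an AE and may never reach the AE form. The later rules cannot repair that. Sections 6.1.2 and 8.8.5 and SAP 10.1 say how long AEs are reported, which are treatment emergent and which treatment they belong to. All three act on events that already count as AEs. They also show that the sponsor wants off-drug events counted, so the closing sentence works against the plan's own intent.

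**Working it through.** **Step 1: the texts side by side.** Take a condition present before first dose that worsens, without becoming serious, after the last dose of a period.

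| Text | Is it an AE? |
|---|---|
| 6.1.1, first bullet | Yes, during or after treatment |
| 6.1.1, closing sentence | Not if the worsening falls outside the treatment period |
| 6.1.2, 8.8.5, SAP 10.1 | Silent; they apply once an event is an AE |

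**Step 2: inputs.**

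- Dosing: two periods of 14 days, 28 days in all (Protocol 3.1).
- Washout: 14 days, window +5, so 14 to 19 (Protocol 3.1).
- Follow-Up: 14 (±3) days after Period 2 Day 14, so 11 to 17 (Protocol 5.1.1.6 and 5.1.2.6).

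The ±1 day on Day 14 and any washout extension approved by the Medical Monitor are ignored.

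**Step 3: reproduce the plan's figure.** 14 + 14 + 14 = 42 days = 6 weeks, which matches the synopsis.

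**Step 4: time left uncovered by the closing sentence.** Total time from first dose to Follow-Up = 28 + washout + follow-up.

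*Reading A, dosing days only.* Share = (washout + follow-up) / total.

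- Nominal: (14 + 14) / 56 = 28/56 = 50%
- Lowest: (14 + 11) / 53 = 25/53 = 47%
- Highest: (19 + 17) / 64 = 36/64 = 56%

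*Reading B, the six-week treatment/study period, washout included.* Share = follow-up / total.

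- Nominal: 14/56 = 25%
- Lowest: 11 / (28 + 19 + 11) = 11/58 = 19%
- Highest: 17 / (28 + 14 + 17) = 17/59 = 29%

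If the first bullet governs, the uncovered time is zero.

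**Step 5: what else would pick up the worsening.** Period 2 Day 1 repeats GDS, ESS, CANTAB, verbal fluency and C-SSRS, with HADS or DCFS by cohort and FOG-Q where it applies. Decline in mood, cognition or gait that persists to the end of the washout is therefore measured whatever its AE status. After Period 2 Day 14 the only visit is Follow-Up. It has vital signs, ECG, laboratory tests, a symptom-driven examination, C-SSRS, concomitant medications and AEs, but no GDS, HADS, DCFS, CANTAB, ESS or FOG-Q. Apart from the C-SSRS, no scheduled scale covers mood, cognition or motor function there.

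**The case against.** The best reply is that the closing sentence is outnumbered. The first bullet, the documentation sentence beside it and the reporting window in 6.1.2 all point to recording through Follow-Up, and the CRF completion guidance, which might settle the matter, is not among the documents. This stands to the extent that loss cannot be stated as fact. It does not remove the conflict, because a reporting window does not decide what qualifies as an AE.

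A second reply is that the sentence uses the singular in a two-period crossover. Protocol 8.5.1 separates entering the treatment period from completing each period, so the singular may mean the whole treatment phase. This also stands, and it is why both readings are sized above. Follow-Up falls outside on either one.

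Three stronger inferences are tempting, and the documents do not support them.

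- *That the SAP attribution rule is contradicted or left with nothing to attribute.* The sentence restricts only illnesses that existed before first dose. New-onset events in the washout and follow-up remain AEs and are attributed as planned.
- *That serious worsening would be missed.* Protocol 6.1.3 requires all serious adverse events to be reported from consent to the final visit.
- *That the safety comparison would flatter the active treatment.* The restriction applies equally after placebo. A bias in that direction needs more worsening after active treatment than after placebo, and the documents give no rates and describe no rebound.

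**Conclusion.** The conflict within Protocol 6.1.1 is real, and no other section resolves it. Its consequence is conditional: non-serious worsening of a pre-existing illness may go unrecorded if a site follows the closing sentence rather than the first bullet. The exposed time is half of the nominal 56 days under Reading A and a quarter under Reading B. These are shares of calendar time, not of events; the number of events at risk cannot be derived from the documents. The follow-up is the weaker stretch, being uncovered on both readings and having the fewest scales behind it. In a descriptive study this is a wording inconsistency in safety recording. It should be corrected because a stated rule can drop events that the plan means to count.

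**What to change.** In the closing sentence of the AE definition in Protocol 6.1.1, replace the last four words with *at any time from first dose through the Follow-Up Visit*. The sentence then agrees, for events after first dose, with its own first bullet, with 6.1.2 and 8.8.5, and with SAP 10.1. Carry the same wording into any CRF completion guidance.

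This does not settle worsening during the Lead-In. Protocol 6.1.2 starts reporting at randomization, 8.8.5 summarizes Lead-In AEs separately, and SAP 10.1 starts at consent, so the start of the window needs its own clarification.

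The cost is one phrase and a few more AE records. No dose, visit, assessment or analysis changes.
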